2.7. RATIONALE FOR THE CHOICE OF DOSE AND DOSING INTERVAL

A dose of 600 mg GLPG1690 administered *q.d.* has been selected to be evaluated for this phase IIa study.

Both preclinical and clinical study results were used to predict an efficacious dose. In the 21-day prophylactic BLM mouse model, GLPG1690's efficacy was reached (in terms of reduction of Ashcroft score) with AUC of 11 $\mu\text{g.h/mL}$, corresponding to 26 $\mu\text{g.h/mL}$ in humans after correction for plasma protein binding. Moreover, a GLPG1690 plasma concentration of 1 $\mu\text{g/mL}$ in healthy subjects allowed triggering maximum LPA 18:2 (PD) biomarker reduction (90%) which could be maintain over 24 hours with an AUC of 24 $\mu\text{g.h/mL}$. Both study results predict GLPG1690's efficacious dose to be around 220 mg.

A dose of 600 mg GLPG1690 *q.d.* is expected to be high enough to reach a plateau in the PD response in a population of subjects with IPF. In addition, 600 mg GLPG1690 is lower than the highest dose assessed in the FIH study in healthy subjects. In this study, administration of single (up to 1500 mg) and multiple ascending oral doses of GLPG1690 (up to 1000 mg *q.d.* for 14 days) in healthy male subjects was considered safe and well tolerated.

3. STUDY OBJECTIVES

3.1. PRIMARY OBJECTIVES

- to evaluate the safety and tolerability of GLPG1690
- to characterize the PK and PD properties of GLPG1690

3.2. SECONDARY OBJECTIVES

- to evaluate the change from baseline in FVC
- to explore the change in biomarkers in blood and BALF
- to evaluate the change in FRI parameters
- to evaluate the change in quality of life measures

4. INVESTIGATIONAL PLAN

4.1. OVERALL STUDY DESIGN

This study is a randomized, double-blind, parallel group, placebo-controlled, multicenter, exploratory phase IIa study to evaluate the safety, tolerability, PK, and PD of GLPG1690 in subjects with IPF. In addition, several exploratory assessments will be performed. Male and female subjects of non-child-bearing potential with a confirmed diagnosis of IPF aged 40 years or older will be screened to determine eligibility as per the inclusion and exclusion criteria (see Section 4.2.2 and 4.2.3, respectively). The screening period will be up to 4 weeks.

Written informed consent must be obtained before any study-related procedures take place. During the screening period, following signing of the informed consent form (ICF), the subject's historical HRCT and surgical lung biopsy (SLB; if available) will be sent to central review for the confirmation of the IPF diagnosis through a:

- central review of the chest HRCT
- central review of the SLB (if available)

Note that both the chest HRCT and SLB need to be sent to central review at least 8 days prior to the baseline visit to allow for central reading and confirmation of IPF diagnosis. Additional details are provided in Appendix 2.

At baseline, after the subject's eligibility for the study has been confirmed, subjects will be randomized in a 3:1 ratio to GLPG1690 600 mg *q.d.* or matching placebo administered for 12 weeks.

The subjects will visit the clinical study center at screening (Day-28 to Day -4), Day -1 (baseline), Week 1 (Day 7), Week 2 (Day 14), Week 4 (Day 28), Week 8 (Day 56), and Week 12 (Day 84) or the early discontinuation visit (EDV). In addition, a follow-up visit will be planned 2 weeks after the last administration of study drug (Week 98 [Day 98]). Each subject will be in the study for up to approximately 18 weeks (from screening to follow-up). The end of the study (EOS) will be defined as the last contact with the last subject in the study.

The assessments performed at each visit are detailed in the study flow chart (Section 1).

To enhance the safety and integrity of the study data, an independent medical safety review will be implemented. (See Section 7 for additional information).

4.2. STUDY POPULATION

4.2.1. Sample Size

Approximately 24 evaluable subjects with a centrally confirmed IPF diagnosis are planned to be randomized.

4.2.2. Inclusion Criteria

Subjects who meet all of the following criteria are eligible for the study:

1. Subjects who are able and willing to sign the ICF as approved by the independent ethics committee (IEC).
2. Male or female subjects of non-child-bearing potential aged ≥ 40 years on the day of signing the ICF.
Note: Female subjects will be considered of non-childbearing potential if they are either sterilized, ovariectomized, hysterectomized, or postmenopausal (*i.e.*, at least 24 months of amenorrhea in the absence of other biological or physiological causes [in case of doubt, the subject's follicle stimulating hormone [FSH] levels will be determined and the subject will be considered postmenopausal if the FSH level is ≥ 35 mIU/mL]).
3. Subjects with a chest HRCT performed within 12 months prior to screening visit.
4. Subjects with IPF diagnosed by a multidisciplinary team and confirmed by central review of the subject's HRCT pattern and SLB (if available) (see Appendix 2 for additional details).
5. Subjects meeting all of the following criteria:
 - a. FVC $\geq 50\%$ predicted of normal
 - b. Diffusing capacity for the lungs for carbon monoxide (DLCO) $\geq 30\%$ predicted of normal (corrected for hemoglobin) (see Appendix 3 for additional details).
6. Subjects with a forced expiratory volume in 1 second (FEV₁)/FVC (Tiffeneau-Pinelli index) ratio ≥ 0.70 (based on pre-bronchodilator spirometry).
7. Subjects who are on stable supportive care (*e.g.*, supplemental oxygen, pulmonary rehabilitation) for at least 3 weeks prior to screening and during screening period.
8. Subjects must be in a stable condition and acceptable for study participation based upon the results of a medical history, physical examination, vital signs, 12-lead ECG, and laboratory evaluation.
9. Subjects must have an estimated minimum life expectancy of 12 months in the opinion of the investigator.
10. Male subjects and their female partners must use a highly effective method of birth control. Additional details on these methods are provided in Section 4.2.4.
11. Subjects who are able to understand the importance of adherence to study treatment, study procedures and requirements, including the concomitant medication restrictions.

4.2.3. Exclusion Criteria

Subjects meeting one or more of the following criteria cannot be selected for this study:

1. Subjects with a known hypersensitivity to any of the study drug ingredients or a history of a significant allergic reaction to any drug as determined by the investigator (*e.g.*, anaphylaxis requiring hospitalization).
2. Subjects with a history of or a current immunosuppressive condition (*e.g.*, human immunodeficiency virus [HIV] infection).
3. Subjects with a history of malignancy within the past 5 years (except for carcinoma *in situ* of the uterine cervix, basal cell carcinoma of the skin that has been treated with no evidence of recurrence, and prostate cancer medically managed through active surveillance or watchful waiting).

4. Subjects with clinically significant abnormalities detected on ECG regarding either rhythm or conduction (e.g., QT interval corrected for heart rate using Fridericia's formula [$QTcF] \geq 450$ ms, or a known long QT syndrome).
Note: A first degree heart block will not be considered as a significant abnormality.
5. Subjects with acute IPF exacerbation within 6 weeks prior to screening and during the screening period.
6. Subject with a lower respiratory tract infection requiring antibiotics within 4 weeks prior to screening and during the screening period.
7. Subjects who have been smoking within 3 months prior to screening.
8. Interstitial lung disease (ILD) associated with known primary diseases (e.g., sarcoidosis, amyloidosis, etc.), exposures (e.g., radiation, silica, asbestos, coal dust, etc.), and drugs (e.g., amiodarone, etc.).
9. Subjects with a history of lung volume reduction surgery or lung transplant.
10. Subjects with an unstable cardiac or pulmonary disease (other than IPF) within 6 months prior to screening or during the screening period, including but not limited to:
 - a. unstable angina pectoris, myocardial infarction
 - b. congestive heart failure requiring hospitalization
11. Subjects with any clinical condition or circumstance that in the opinion of the investigator may make a subject unsuitable for inclusion or unable to complete the study or comply with study procedures and requirements.
12. Subjects with a contra-indication for bronchoscopy and bronchoalveolar lavage in the opinion of the investigator.
13. Subjects with an abnormal liver function defined as aspartate aminotransferase (AST), alanine aminotransferase (ALT), or bilirubin >3 x upper limit of the normal range (ULN).
14. Subjects with an abnormal renal function defined as creatinine clearance < 50 mL/min using the Cockcroft-Gault equation.
15. Subjects participating in a drug/device or biologic investigational research study (concurrently with the current study or within 8 weeks prior to screening).
16. Subjects using of any of the following therapies within 4 weeks before screening:
 - a. Pirfenidone
 - b. Nintedanib
 - c. Warfarin
 - d. Imatinib
 - e. Ambrisentan
 - f. Azathioprine
 - g. Cyclophosphamide
 - h. Cyclosporine A
 - i. Prednisone at steady dose > 15 mg/day (for details, see Section 4.2.4)
 - j. Any experimental IPF therapy
17. Subjects with active alcohol or substance abuse in the opinion of the investigator.

4.2.4. Prohibition and Restrictions

Smoking is forbidden at all times (from 3 months before screening to the end of the study).

The following therapies are not allowed during the course of the study (and within 4 weeks prior to screening): pirfenidone, nintedanib, warfarin, imatinib, ambrisentan, azathioprine, cyclophosphamide, cyclosporine A, prednisone at steady dose > 15 mg/day (*i.e.*, the use of prednisone is precluded unless subjects have been on a stable dose ≤ 15 mg daily and it is anticipated that they will continue on this stable dose for the duration of the study), and any experimental IPF therapy.

Male subjects and their female partners must use 2 generally accepted adequate contraceptive methods, 1 of which is a barrier method (*e.g.*, condom in combination with hormonal contraception stabilized for at least 1 month) from screening until 3 months after the study. In addition, sperm donation is not allowed until 3 months after the last study visit. In a case where the female partner of a male subject has undergone documented surgical sterilization that was performed more than 1 year before screening, the subject is not required to use an additional form of contraception.

4.2.5. Removal of Subjects from Therapy or Assessments

A subject may be discontinued from the study at any time without the subject's consent if the investigator or sponsor determines that it is not in the best interest of the subject to continue participation.

Subjects may withdraw from the study at any time, for any reason, without jeopardizing their clinical care.

Subjects **may be withdrawn from the study** for any of the following reasons:

- noncompliance with the study drug
- noncompliance with the study procedures
- lost to follow-up
- SAEs or severe AEs can be considered a reason for discontinuation of treatment, preferably after consultation with the medical monitor
- investigator request
- sponsor request

A subject **may be withdrawn from the study after discussion between the investigator and the medical monitor** for any of the following reasons:

- use of concurrent therapy that was not permitted
- prolonged interruption of study drug (*i.e.*, interruption > 7 days)
- life-threatening AE or an SAE that places the subject at immediate risk
- increase in liver function tests (LFTs) to $3 \times$ ULN (if the baseline LFTs are normal) or an increase that exceeds an absolute value of $5 \times$ ULN (regardless of whether baseline LFTs are normal)

A subject **must be withdrawn from the study** for any of the following reasons:

- serious infections (those requiring parenteral antimicrobial therapy and/or hospitalization)

- arrhythmia or conduction abnormality (including but not limited to prolonged QTcF, where the severity is categorized as Common Terminology Criteria for Adverse Events [CTCAE] grade 3 or higher)
- clinical laboratory test results, which are determined by the investigator in consultation with the medical monitor to be clinically significant and require discontinuation of study drug; changes in LFTs are defined as follows (confirmed upon repeat testing):
 - elevated ALT or AST of $> 8 \times \text{ULN}$
 - elevated ALT or AST of $> 5 \times \text{ULN}$ for > 2 weeks
 - total bilirubin $> 2 \times \text{ULN}$ and/or clinical jaundice, in association with elevation of ALT or AST $> 3 \times \text{ULN}$
 - no convincing alternative etiology (e.g., viral hepatitis, alcohol ingestion, trauma) for the elevated transaminase is identified, regardless of whether ALT or AST levels had improved
- unblinding of a subject's study treatment assignment to the subject, the site staff, or the blinded sponsor staff while on study drug
- close of the study by the sponsor or regulatory authorities
- wish of the subject to withdraw (At any time and for any reason, a subject's participation in the study may terminate at his/her request without prejudice to his/her future medical care.)
- worsening of the subject's disease condition, which in the investigator's opinion needs an alternative treatment approach

In case clinically significant laboratory test results are a potential reason for discontinuation from the study drug and withdrawal from the study, retesting should be prompted (within 3 to 5 days) after the investigator has consulted with the medical monitor. A decision regarding subject discontinuation should be made only after the results from the retest are available.

Subjects who stop study drug for any reason will not be replaced. Subjects withdrawing from the study will be encouraged to complete the same final evaluations as subjects completing the study according to the protocol, particularly safety evaluations in the subject's interest so that data can be recorded in the same way as for subjects who completed the study. The reason(s) for withdrawal will be documented in the electronic case report form (eCRF). Note that randomized subjects who drop out before the first administration of the study drug will be replaced.

Reasonable efforts (3 attempts) will be made to get confirmation on the reasons for dropout for subjects who are lost to follow-up. These attempts must be documented in the subject's file.

The sponsor has the right to terminate the study at any time in case of safety concerns or if special circumstances concerning the study drug or the company itself occur, making further treatment of subjects impossible. In this event, the investigator(s) and relevant authorities will be informed of the reason for study termination.

4.3. INVESTIGATIONS MEDICINAL PRODUCTS

4.3.1. Identity of the Investigations Medicinal Products

The study drug GLPG1690 will be supplied to the study center, by and under the responsibility of the sponsor, who will also provide the investigator with appropriate certificates of analytical conformity and EU QP release documents.

The study drug GLPG1690 will be presented as oral capsules (size 00), containing 200 mg G451990 (G451990 is the compound code for GLPG1690). The placebo will be provided as a matching capsule.

A full list of excipients used in the oral capsule formulation is available in the Investigator's Brochure. (Investigator Brochure GLPG1690, Edition 2, October 2015) At the investigational site, the study drug supplies must be handled and stored safely and properly, and kept in a secured location to which only the investigator and authorized staff have access.

4.3.2. Dosage and Administration

A dose of 600 mg *q.d.* or placebo *q.d.*, administered in the morning, will be evaluated. Subjects will receive 600 mg GLPG1690 (3 capsules of 200 mg) or placebo *q.d.* for 12 weeks.

Study drug dosing will take place at the time points indicated in the study flow chart (Section 1). When dosing takes place at the clinical study center, a volume of 240 mL water will be provided to each subject to be consumed immediately and completely at the time of dosing. Subjects will be instructed to swallow the study drug whole, and not chew the drug prior to swallowing.

If a subject misses a dose (*e.g.*, because he/she forgot to take the medication), he/she should take the missed dose within 12 hours after the planned intake time. If the study drug is not taken within 12 hours after the planned time, the missed dose should be skipped.

Dose changes during the study are not allowed. Instead, the subject should either temporarily stop all intake or permanently stop study drug. Every effort should be made to contact the medical monitor before stopping study drug (temporarily or permanently).

4.3.3. Randomization

A total of approximately 24 subjects will be randomized in a 3:1 allocation ratio to active treatment with GLPG1690 or placebo.

Allocation of each subject to a given treatment will be described in a randomization list prepared by the CRO. This randomization list will be created using permuted blocks. Upon qualification for the study, subjects will be randomized using a computerized interactive voice/web response system (████████) to placebo or GLPG1690.

For each subject at each visit, the study center will contact the ██████████ system for the appropriate treatment number to be dispensed. Each medication kit will contain the relevant study drug for the period until the next visit.

Subjects and study personnel will be blinded to the treatment assignment. Additional details on blinding and unblinding are provided in Section 4.3.8.

4.3.4. Packaging, Labeling, and Distribution

The study drug packaging, labeling, QP release, and distribution will be performed by [REDACTED] (Belgium). Study drug manufacturing will be performed by [REDACTED] (Belgium).

The oral capsules will be packaged in high density polyethylene bottles with a high density polyethylene closure and grouped in a carton box for shipment.

All manufacturing, packaging, and labeling operations will be performed according to Good Manufacturing Practices for Medicinal Products and the relevant regulatory requirements.

The study drug is to be dispensed according to the protocol. The distribution will only occur after all required documentation is obtained including study approval by the Competent Authorities and the IEC.

Each medication kit will be identified with a unique kit number and will contain sufficient capsules for the subject until the next scheduled study visit. The medication kits will be labeled according to local requirements.

4.3.5. Storage

Sites are to store all drug supplies in a secured location to which only the investigator and authorized staff have access.

Study drug must be stored at room temperature (15-25°C). Sites will be required to monitor the storage temperature by using a min-max temperature-recording device and to keep a temperature log, completed each working day, to establish a record of compliance with storage conditions. The investigator will instruct subjects on how to store the study drug after it has been dispensed.

In accordance with the International Conference on Harmonization (ICH) Good Clinical Practice (GCP), the investigator will be responsible for the monitoring, receipt, storage, dispensing, and accounting of all study drug supplies according to accepted medical and pharmaceutical practice. All details of study drug supplies receipt, storage, administration and return will be recorded and the records must be retained in the investigator's site file. Accurate site records of drug inventory and dispensing must be maintained. All records must be made available to Galapagos, the contract research organization (CRO), and appropriate regulatory agencies upon request. At the end of the study, this record will be checked against all used and unused medication by the monitor.

4.3.6. Treatment Compliance and Drug Accountability

For each dose taken, the date, time and number of capsules taken should be recorded on the subject's diary card (see Section 5.3 for additional information).

The investigator or designated study personnel will maintain a log of all study drug dispensed and returned. Drug supplies for each subject will be inventoried and accounted for throughout the study. All clinical supplies will be stored in locked facilities.

Subjects will return any unused study drug and empty bottles at each study visit and/or early discontinuation visit (if applicable). Missed doses should be discussed to try to ascertain the reason(s). Every effort should be made to ensure proper subject dosing.

All unused medication and empty bottles will be returned to the drug supplier/CRO depot as applicable at the closure of the study site or will be destroyed at the site, upon sponsor decision.

4.3.7. Prior and Concomitant Therapy

Should any treatment other than the study drug be used during the course of the study, the name of the drug, the dosage, the route, and the dates (and time) of administration must be recorded in the eCRF system. Prior and concomitant medications (taken up to 8 weeks prior to Day 1) will be recorded from the study inclusion date (ICF signed) until the last visit.

Concomitant therapies taken for the long-term treatment of preexisting conditions can continue during the study provided they are in accordance with the inclusion and exclusion criteria (see Section 4.2.2 and Section 4.2.3, respectively). It is required that these medications be stabilized prior to study entry and continued without variation of dose or regimen during the study.

In a case additional concomitant medication needs to be administered or dose adjustments for preexisting conditions need to be performed during the study, the risk/benefit to the subject should be carefully assessed and consideration given to the timing of any necessary introduction of new medications. It is recommended that the medical monitor is contacted to check if the subject could be included in the study or if some of the concomitant drugs should be stopped and/or replaced.

If the subject shows a worsening of his/her IPF disease condition (acute IPF exacerbation), all treatment options are allowed at the investigator's discretion. The decision to continue treatment with study drug should be taken on a case-by-case basis, preferably after discussion with the study's medical monitor.

Drug-drug Interactions

The only CYP enzyme involved in GLPG1690 metabolism is CYP3A4. Therefore, caution should be exercised when coadministering GLPG1690 with drugs/nutraceuticals known as CYP3A4 inducer in order to ascertain GLPG1690 exposure. A (non-exhaustive) list of CYP3A4 inducers is provided in Appendix 4.

In vitro interaction studies of GLPG1690 with CYPs showed some degree of inhibition, with IC_{50} values \geq 13-fold the free steady state C_{max} expected in human after a 600 mg dose, as well as some induction at concentrations \geq 60-fold the expected free steady state C_{max} . Towards key drug transporters, some inhibition by GLPG1690 was observed, with IC_{50} values \geq 7-fold the free steady state C_{max} expected in human after a 600 mg dose. Therefore, it can be concluded that drug-drug interactions with GLPG1690 are unlikely. However, in case of coadministration of drugs with narrow therapeutic index, like warfarin, theophylline, or digoxin, precautions and specific monitoring should be considered.

It is recommended that the medical monitor is contacted to check whether the subject could be included in the study or if some of the concomitant drugs/nutraceuticals should be stopped and/or replaced prior to dosing with GLPG1690.

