2.3.3. Nonclinical Pharmacokinetics and Product Metabolism

The absolute oral bioavailability was moderate in rodents (25-36%), low in monkeys (14%), and high in dogs (102%).

GLPG1690 was highly bound to plasma proteins: 99.1% in human and 97.9-99.6% in rat, dog, mouse, rabbit, and monkey.

Overall, GLPG1690 did not extensively distribute into tissues as shown by the low volume of distribution (V_{ss}) ranging from 0.35 L/kg in the mouse to 0.55 L/kg in the monkey.

Upon repeated once daily (*q.d.*) oral dosing of GLPG1690, no significant accumulation was observed in the rat and some accumulation (up to approximately 9-fold) was observed in the dog at the highest tested dose of 100 mg/kg/day. Gender differences in PK profiles were observed in rats but not in dogs.

The total plasma clearance (Cl) of GLPG1690 was low in mice, rats, monkeys, and dogs, ranging between 3 and 23% of the hepatic blood flow. Therefore, GLPG1690 is expected to undergo a low first-pass effect after oral dosing.

The only cytochrome P450 (CYP) enzyme involved in GLPG1690 metabolism was CYP3A4. *In vitro* metabolism studies in hepatocytes revealed 26 potential metabolites. Metabolites formed in human hepatocytes were all present to a similar or higher extent in rat and/or dog hepatocytes, the animal species selected for toxicity studies. In human, 8 metabolites resulting from hydrolysis, hydroxylation, addition of water, demethylation, or reduction were detected in plasma and/or urine. These metabolites were also observed in rat and dog plasma.

In vitro interaction studies of GLPG1690 with CYPs showed some degree of inhibition, with IC_{50} values \geq 13-fold the free steady state maximum plasma concentration (C_{max}) expected in human after a 600 mg dose, as well as some induction at concentrations \geq 60-fold the expected free steady state C_{max} . Towards key drug transporters, some inhibition by GLPG1690 was observed, with IC_{50} values \geq 7-fold the free steady state C_{max} expected in human after a 600 mg dose. Therefore, it can be concluded that drug-drug interactions with GLPG1690 are unlikely.

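### The interaction guidance in Section 4.3.7 covers CYP3A4 inducers but not inhibitors, and its conclusion that interactions are unlikely is wider than the evidence given for it

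*Protocol*

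**What the plan says.** **Route of metabolism.** Section 2.3.3 says: "The only cytochrome P450 (CYP) enzyme involved in GLPG1690 metabolism was CYP3A4". Section 4.3.7 repeats this at the start of its drug-drug interaction text.

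**Caution drawn from it.** Section 4.3.7 continues: "caution should be exercised when coadministering GLPG1690 with drugs/nutraceuticals known as CYP3A4 inducer in order to ascertain GLPG1690 exposure". It refers to Appendix 4, which is a list of inducers with no counterpart for inhibitors.

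**Conclusion on interactions.** After in vitro results for GLPG1690 acting on CYPs and on transporters, Section 4.3.7 states: "Therefore, it can be concluded that drug-drug interactions with GLPG1690 are unlikely". Section 2.3.3 draws the same conclusion from the same data. The one other specific caution is for co-medications with a narrow therapeutic index.

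**Rules on co-medication (Section 4.3.7).** Long-term therapies compatible with the entry criteria may continue, and must be stabilised before entry and "continued without variation of dose or regimen during the study". For added drugs or dose adjustments, the investigator weighs risk and benefit and is advised to contact the medical monitor. A separate recommendation closes the section: contact the monitor about eligibility and about stopping or replacing concomitant drugs before dosing starts. In an acute exacerbation, "all treatment options are allowed at the investigator's discretion", and continuing study drug is decided case by case.

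**Dose.** Section 4.3.2: "Dose changes during the study are not allowed".

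**The concern.** If one enzyme is the only CYP clearing a drug, co-medication can move exposure both ways: inducers can lower it and inhibitors can raise it. The protocol starts from that premise and follows one direction. CYP3A4 inhibitors as co-medication are not mentioned in Sections 4.2.3, 4.2.4 or 4.3.7 or in Appendix 4. A site is then told, without limitation, that interactions are unlikely.

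Two things are at stake. The first is safety margin. Repeated human dosing had reached 1000 mg once daily for 14 days in healthy men (Section 2.4), whereas this trial doses patients with IPF for 12 weeks at a fixed 600 mg. The second is the PK objective in Section 3.1. With 24 subjects at 3:1, about 24 × 3/4 = 18 receive active drug. Section 6.2.4 removes subjects from the PK set for deviations that may affect PK, but permitted use of an inhibitor is not plainly a deviation. A subject with altered exposure could therefore stay in the summary.

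**Working it through.** **Step 1. Match each statement to its direction of effect.**

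| Statement | Effect of other drugs on GLPG1690 | Effect of GLPG1690 on other drugs |
|---|---|---|
| CYP3A4 is the only CYP involved (2.3.3, 4.3.7) | premise, both inducers and inhibitors | – |
| Inducer caution and Appendix 4 | inducers only | – |
| CYP inhibition at ≥13-fold, CYP induction at ≥60-fold, transporter inhibition at ≥7-fold free Cmax | – | yes |
| Narrow-therapeutic-index caution | – | yes |
| Interactions unlikely | wording not limited | supported by the row on in vitro data |

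No row addresses a CYP3A4 inhibitor raising GLPG1690. The tested CYPs are not named and may include CYP3A4, but the results still describe GLPG1690 as the agent acting, not as the drug acted upon.

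**Step 2. Follow the two routes by which an inhibitor could be present.** For a stable co-medication, the continuation rule applies and the closing recommendation in 4.3.7 invites a call to the monitor. For a newly started drug, the risk/benefit sentence and its monitor recommendation apply. Both give a chance to catch the problem, but neither says that an inhibitor is a reason to call. Section 4.2.5 requires withdrawal for infections needing parenteral antimicrobials or hospitalisation, and for worsening that needs a different treatment approach. That narrows the exacerbation route. It does not reach stable co-medication or oral outpatient courses.

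**Step 3. Scale, under assumptions.** The protocol gives no CYP3A4 share of clearance. Let fm be that share and I the fraction of the pathway inhibited; both are assumed. First-pass and absorption are taken as unchanged, in line with Section 2.3.3: "GLPG1690 is expected to undergo a low first-pass effect after oral dosing".

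AUC ratio = 1 / (1 − fm × I)

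*Human reference.* Exposure is dose-proportional from 300 to 1000 mg daily (Section 2.4), so the highest repeated dose corresponds to 1000/600 = 1.67 times study exposure. It is exceeded when fm × I > 1 − 600/1000 = 0.40:

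- I = 1: fm > 0.40
- I = 0.8: fm > 0.50
- I = 0.5: fm > 0.80

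*Animal reference.* Section 2.3.4.1 gives 13-week NOAEL ratios at 600 mg of about 0.9 (male rat), 21 (dog) and 22 (female rat). Dividing each by the AUC ratio at I = 1:

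| Assumed fm | AUC ratio | Male rat | Dog | Female rat |
|---|---|---|---|---|
| none | 1.00 | 0.9 | 21 | 22 |
| 0.10 | 1.11 | 0.81 | 18.9 | 19.8 |
| 0.25 | 1.33 | 0.68 | 15.8 | 16.5 |
| 0.40 | 1.67 | 0.54 | 12.6 | 13.2 |

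The male-rat ratio is below 1 before any inhibitor is added, so these figures do not mark a threshold newly crossed. They show how the stated margins would move.

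**The case against.** The strongest reply is that the protocol already has a catch-all. The recommendation at the end of Section 4.3.7 is not limited to inducers, applies before dosing, and covers whether a concomitant drug should be stopped or swapped. A physician told that CYP3A4 is the only CYP involved may also think of inhibitors unprompted. This stands in part: a reader might infer that inhibitors are wholly unguarded, and the text does not support that. But the advice is general, is only recommended, and sits beside an inducer-only list and the statement that interactions are unlikely.

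A reader might also infer from the bar on dose changes that raised exposure leaves nothing to do but interrupt or stop study drug. That is wrong. Section 4.3.7 also allows the co-medication to be stopped or replaced.

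It can be argued that the unlikely statement, following directly on the in vitro results, refers to GLPG1690's effects alone, since the preceding paragraph treats the inducer question separately. That is a fair reading of intent, but the wording does not say so.

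Finally, clinical weight is not shown. Section 2.5 predicts low metabolism and mainly fecal elimination, and doses above 600 mg were described as well tolerated. PK samples, laboratory tests and ECGs are scheduled at every on-treatment visit, co-medication is recorded, and an independent expert reviews unblinded safety data (Section 7). All of this stands and holds the severity down. It does not justify the omission: the low-metabolism statement is offered to support dosing elderly subjects, and it puts no figure on the CYP3A4 share.

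**Conclusion.** The point holds as a one-sided rule. The protocol's own premise about CYP3A4 calls for a caution on inhibitors as well as inducers, and the evidence cited for the unlikely statement bears only on GLPG1690's effects on other drugs. The existing medical-monitor recommendations give partial cover without identifying inhibitors as a reason for contact.

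The size of any exposure rise cannot be derived from the protocol and may be small. The 1.67-fold human reference would be passed only under the assumed combinations of fm and inhibition shown above, and none of those fm values comes from the document. A reader might take the margin table as evidence of overexposure or of a safety hazard; it is neither.

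The conclusion concerns the protocol text alone. The Investigator's Brochure, to which the protocol refers for further information, is not at hand and may contain guidance on inhibitors. Severity is low; this is a cheap improvement worth making.

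**What to change.** - In Section 4.3.7, name CYP3A4 inhibitors, at least strong ones, alongside inducers in the caution. Make them an explicit trigger for the medical-monitor contact already recommended, both at entry and before one is started on study drug, including exacerbation care if study drug continues.
- Add a short, non-exhaustive inhibitor list to Appendix 4.
- In Sections 2.3.3 and 4.3.7, limit the unlikely statement to effects of GLPG1690 on other drugs.
- Keep the inducer caution as it is. Whether any inhibitor should be restricted outright is for the sponsor to decide.

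The cost is a few sentences, one list and some additional medical-monitor queries. No new data or procedures are needed.
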